10.3 Data and Safety Monitoring Procedure and Plan

An external **Data Safety and Monitoring Board (DSMB)** is appointed by and reports to the NINDS. Open and closed reports will be prepared by the NETT-SDMC statisticians. The DSMB will meet approximately every 6 months with additional meetings scheduled as they require. At intervals defined by the DSMB, reports of safety events will be submitted to the DSMB by NETT-SDMC statisticians.

A blinded **Clinician Event Coordinator** will review safety data on SAEs as they become available to the UCSF CCC, including adjudicating whether events are serious, related to the study drug, or unexpected (in addition to the review of the site investigator). The safety data will be made available to the Clinician Event Coordinator on the WebDCU™ system to allow real-time access, review and reporting.

10.3.1 Interim Analyses and Stopping Rules

Unacceptable Safety Profile. The DSMB will be asked to use judgment to weigh evidence of efficacy and rates of adverse events. The committee will meet, as outlined in NINDS guidelines, to assure subject safety; additional interim analyses may be requested by the DSMB. Since frequency, severity, and distribution of adverse events, as well as early evidence of benefit, are all likely to affect the decision to discontinue a treatment arm, establishing strict criteria for stopping *a priori* is imprudent; rather, careful judgment of the DSMB will be required.

Superiority or Inferiority Established Prematurely. The number of interim evaluations of the primary outcome data will be determined by the DSMB and will be described in the Statistical Analysis Plan.

11 ETHICAL AND REGULATORY STANDARDS

11.1 Ethical Considerations

The study will be conducted in accordance with the U.S. Food and Drug Administration's (FDA) Code of Federal Regulations (CFR Title 21), ICH Good Clinical Practice (GCP) guidelines, and the relevant regulations for clinical trials for each investigational site.

11.2 Regulatory Requirements

Prior to initiating the study, each site will obtain IRB or Ethics Committee approval for the protocol, Informed Consent Forms and materials used to recruit subjects. In addition, each investigator will sign an Investigator Agreement with the study sponsor. IRB/IEC-approved informational videos and quizzes designed to inform physicians and supplement the informed consent process may be presented on tablet devices and online to study physicians and potential subjects. Signatures of study subjects documenting their consent will be collected on paper and/or digitally. Prior to their participation, subjects will be provided printed paper copies of the signed consent form, as required by ICH GCP 4.8.11 and 21 CFR 50.27. Protocol amendments are not allowed by any investigator without prior approval from the Executive Committee. All changes to the protocol approved by the Executive Committee must be submitted to the site's IRB/IEC for review and approval as appropriate. The trial has received a waiver from IND requirements from the FDA. However, each investigator at sites outside the U.S. must assure that any necessary approvals, or applicable waiver(s), have been obtained from the appropriate regulatory authority and/or national competent health authority, with authorization to proceed.

11.3 Institutional Review Board (IRB) or Ethics Committee (EC)

Prior to initiating the study, each Investigator must submit the following to an IRB/IEC: the Informed Consent Form, this protocol and materials used to recruit subjects for this clinical trial. No study subjects may be recruited until documented IRB/IEC approval (or favorable opinion) is obtained for that site. Any addendums or revisions to the above documents must be resubmitted for review and approval. Each investigator will follow the requirements of his or her IRB/IEC on periodic reporting of the progress of the study, reporting of serious or unexpected adverse events, safety monitoring reports, and termination of the study.

11.4 Informed Consent

Each eligible patient who wishes to participate in this study will be required to give written informed consent. Written informed consent will include signatures collected on paper and/or digitally and subjects will be provided printed paper copies of the consent form. Before the consent form is signed, a trained researcher will explain why the patient was selected for screening and the purpose of the

screening and how results of screening are used to determine eligibility. IRB/IEC-approved informational videos and quizzes designed to inform physicians and supplement the informed consent process may be presented online, and on tablet or similar electronic devices to study physicians and patients. The patient will be informed that, if he or she meets all of the inclusion criteria and none of the exclusion criteria, and agrees to participate, he or she will be enrolled in a clinical trial of clopidogrel and placebo. The consent document explains the risks and potential benefits of the therapy, the procedures for the trial, and alternatives to participation. There will be no surrogate consent in the study. Subjects must personally consent to participation and sign the approved consent form(s) which will be retained by the investigator and may be reviewed by the sponsor's authorized monitors or auditors, and authorized representatives from regulatory authorities.

12 STUDY MONITORING

12.1 Site Monitoring, Quality Assurance and Remedial Actions

Quality Assurance activities will be a collaborative effort between the POINT CRC and the NETT CCC.

12.1.1 Site Visits

The POINT CRC monitoring staff or contractors will perform all site visits to CRC investigators, on a jointly acceptable schedule. Similarly, the NETT-CCC will perform all visits for its sites. The site Readiness Call will take place via telephone contact prior to any participants being enrolled. Required regulatory documents will be stored in the regulatory module of WebDCU™. Subsequent site visits are scheduled on an as-needed basis based on recruitment, data quality, or continued noncompliance (for cause). Every site will receive at least one visit during the course of the study. The visit will include review of regulatory documents maintained at the site, verification of the appropriate version and completion of Informed Consent Forms, supplemental videos and quizzes, protocol compliance, study drug accountability, discussions with the site PI and staff regarding study conduct, and a data audit against source documents, as available. The site visits will follow the CRC and NETT Standard Operating Procedures/Monitoring Plan for conducting visits. A site visit report summarizing the findings will be issued to the Study PI and the Operations Committee within 28 days of the visit.

12.1.2 Remedial Action

Sites that demonstrate difficulty complying with study procedures, recruitment, or maintaining data quality will be discussed with the Executive Committee. Action may include direct phone contact with the site PI by the POINT CRC or NETT Site Monitor to discuss the issues and create a corrective action plan, subsequent site visit by the Site Monitor, and/or a probationary period until effective corrective action has been taken. If the situation remains unresolved, the Executive Committee may suspend the site from the study. Specifically, with regard to recruitment, sites that are certified to enroll study participants but do not enroll a participant in 90 days, will be contacted by the CRC or NETT Site Monitor via telephone to determine the site's continued interest in study participation, and to create a plan to increase enrollment of participants.

12.2 Data Management

12.2.1 Data Quality Monitoring

The POINT CRC monitoring staff will have access to real-time data that describe the quality of the data submitted by CRC physicians, and the NETT CCC will do the same for its sites. These data include recruitment, missing values and other data anomalies, missing forms, missed visits, late visits, subject ineligibility post enrollment, and other protocol deviations and violations.

13 PUBLICATION OF RESEARCH FINDINGS

Publication of the results of this trial will be governed by the policies and procedures developed by the Executive Committee. The trial results will be published as soon as possible after database lockdown.

This trial will produce detailed data on treatment effects, medical care, and outcomes in a cohort of 5,840 subjects with TIA or minor ischemic stroke. Three years after the primary publication associated with this work is submitted, a HIPAA-compliant, de-identified version of the database will be made available publicly. POINT biostatisticians will be consulted to assure that it is impossible to uniquely identify any participant. This may mean removing or categorizing certain variables. A data use agreement will not be required for access to this dataset. Data in comma-delimited text format will be sent to parties that express interest, including a data dictionary in a text file.

The goal of the POINT Trial Publications Policy is to provide guidelines for preparing, reviewing, submitting and maximizing productivity of high-quality peer-reviewed publications. In addition to overseeing the performance of the trial, the Executive Committee is responsible for encouraging paper production, ensuring timely publication of data, maintaining a high standard for the quality of papers produced for POINT, and determining appropriate authorship. When the Committee is discussing manuscripts associated with ancillary studies, the PI of the ancillary study and his/her designee will also join the Executive Committee for that discussion (see Section 14, Ancillary Studies).

Manuscript proposals will be submitted to the Executive Committee. These proposals will include the type (primary, secondary, tertiary and quaternary), list of authors and their qualifications for authorship, a statement that no others deserving authorship have been omitted, the scientific rationale for the paper, the data needed and a description of the proposed analyses and any deadlines for submission of abstracts or presentation dates if applicable. The Publications Policy can be found in the Manual of Procedures.

14 ANCILLARY STUDIES

Proposals for ancillary studies will be reviewed by the Executive Committee; these studies will require funding outside the original study grant. The committee will assure that all such studies are hypothesis driven, methodologically robust and contain complete and accurate data. Approval will follow the ancillary study approval process which defines the standard procedures for proposing, reviewing, and approving ancillary studies and/or substudies conducted within the trial. It will meet each month by teleconference the first 6 months of enrollment, and every other month for the duration of subject enrollment.

Pharmaceutical industry representatives have not been involved with the trial design and will not participate routinely in the execution of the trial or presentation of the results. Data will be controlled by the Executive Committee, which will review requests for access and specific analyses. Monitoring during the trial will be dictated by safety and scientific concerns rather than regulatory requirements. Publication of the results will be governed by the policies and procedures developed by the Executive Committee. Sites will not be required to participate in any ancillary study that requires additional data collection, but they will be encouraged to participate in accepted studies. The Ancillary Studies Policy can be found in the Manual of Procedures.

14.1 Optional POINT Biomarkers Ancillary Study

Participants who consent to the POINT trial will be asked to consent to an optional ancillary study consisting of a one-time venous blood sample of approximately 10 mL, collected at the time of enrollment in the trial. Subjects indicating consent to the Biomarkers Study by checking the appropriate box will be asked for a one-time sample of approximately 10 mL of peripheral venous blood. Consent will be collected for both the blood sample and the optional ancillary study. Those patients who decline the ancillary study will not be prohibited from participating in the POINT Trial.

Plasma and DNA will be prepared for genotyping analysis and stored at the Neurogenetics Laboratory at the Mayo Clinic in Jacksonville, Florida (MCF) as required by Federal and state regulations. The study samples will be used for testing the specific hypothesis as to whether clopidogrel resistant genotypes modify the stroke prevention response in high-risk TIA patients. Subjects will be assigned numbers which will be placed on the sample labels and allow researchers to link the sample to the encrypted ancillary study database. No personal identifying information will be kept with the samples. Results of the genotyping analysis will not be shared with subjects.

Of primary interest is the relative risk of vascular outcome events for carriers (of specific ABCB1 and CYP2C19 genotypes) versus non-carriers amongst those receiving clopidogrel. Of secondary interest is a subgroup analysis by the enrolling/index event type (either TIA or minor ischemic stroke cohort) performed separately for the TIA cohort and the minor ischemic stroke cohort.

Genotyping results (raw data and summary data) will be provided to the POINT Trial Principal Investigator and lead statistician for incorporation into the existing trial data set into WebDCU. Analyses exploring an interaction between genotypes and treatment response will be done jointly, including testing of inherited clopidogrel resistance. This would be the first systematic study of clopidogrel resistance in the setting of stroke prevention following TIA. The stored samples will also be a resource for future studies in this patient population.

### 1 LIST OF ABBREVIATIONS

AE Adverse Event
CRF Case Report Form

DCR Data Clarification Request
DCU Data Coordination Unit

DSMB Data Safety and Monitoring Board

FASTER Fast Assessment of Stroke and Transient ischemic attack to prevent

Early Recurrence

GCP Good Clinical Practice

HR Hazard Ratio
ITT Intent-to-Treat
MI Myocardial Infarction

NETT Neurological Emergencies Treatment Trials
NIHSS National Institutes of Health Stroke Score

NINDS National Institute of Neurological Disorders and Stroke

POINT Platelet-Oriented Inhibition in New TIA and minor ischemic stroke

SAE Serious Adverse Event

SDMC Statistical and Data Management Center

TIA Transient Ischemic Attack

### 2 STATISTICAL ANALYSIS PLAN AND STATISTICAL REPORTS

This document provides the details of statistical analyses planned for the POINT Trial, including interim analyses for efficacy and evaluation of futility. In addition, it discusses the statistical issues relevant to these analyses (e.g., sample data to be used, missing data, adjustments for multiplicity, etc.)

The NETT SDMC will generate Data and Safety Monitoring (DSMB) Reports semiannually or more frequently upon request by the DSMB. Each semiannual report provides cumulative summary statistics on enrollment; subject status in the study (e.g., number completed day 7 and day 90 assessments); baseline characteristics; protocol violations; safety data, including coded SAEs, clinical outcomes data (with primary outcomes following the interim analysis schedule listed in section 12.2); and data management/quality information (e.g., timeliness and completeness of data entry by the clinical centers via the POINT Trial web-enabled clinical trials management system (WebDCU™); number of data queries generated and resolved). For all safety data, tables or figures will be stratified according to index event type: either TIA or minor stroke. The statistics for the 'Closed Session' DSMB Reports are provided by treatment group (partially blinded). The 'Open Session' DSMB report contains aggregated statistics only, i.e., not by treatment group. If a semiannual report coincides in timing with a planned interim analysis, the analysis results are appended to the report.

### 3 OBJECTIVES OF THE STUDY

### 3.1. Efficacy

The primary objective of the POINT Trial is to determine the effectiveness of clopidogrel (a loading dose of 600 mg followed by 75 mg/day) over placebo when initiated within 12 hours of time last known free of new ischemic symptoms in patients receiving aspirin therapy at 50-325 mg/day. The primary efficacy hypothesis is that event-free survival at 90 days is higher in subjects treated with clopidogrel+aspirin than in subjects treated with placebo+aspirin, when randomized within 12 hours of time last known free of new ischemic symptoms. The primary outcome measure for this hypothesis is the composite event of ischemic stroke, MI, or ischemic vascular death.

### 3.2. Safety

The safety of clopidogrel when compared to placebo is evaluated by comparing rates of allcause death, intracranial hemorrhage, major hemorrhage, minor hemorrhage, and other treatment related complications and SAEs (see section 13.2).

The primary safety outcome is major hemorrhage. Major hemorrhage is one that results in symptomatic intracranial hemorrhage, intraocular bleeding causing loss of vision, need for transfusion of two or more units of red cells or equivalent amount of whole blood, need for hospitalization or prolongation of an existing hospitalization, or death. This may include bleeding events related to surgical procedures.

### 4 STUDY DESIGN

The study is of a two-arm parallel design whereby eligible subjects are randomized in a 1:1 ratio to either the clopidogrel group or to the placebo group. Each subject is followed for 90 days from randomization.

### 5 SAMPLE SIZE CONSIDERATIONS

### 5.1 Sample Size Determination for the primary efficacy Analysis

The minimum necessary sample size in the trial is established by the requirement to detect the smallest expected, clinically meaningful treatment difference comparing the treatment with placebo. A relative risk reduction of 23% is the smallest difference felt to be of clinical importance. The total sample size for the study is 4,150 subjects (rounded up from 4,142). With a sample size of 4,150 patients, with 530 events, the study will have 90% power to detect a relative risk reduction of 23% with a two-sided alpha of 0.05. The sample size was estimated based on a hazard ratio (HR) of 0.75 (equivalent to RRR of 23%) assuming an exponential survival distribution (assuming the proportion of patients with events in the placebo group is 0.1524 at 90 days), with inflation to account for two interim analysis for efficacy at equal intervals using O'Brien and Fleming stopping boundary using the Lan-Demets spending function and inflation for lost-to-follow-up and/or crossover. The intent-to-treat (ITT) principle is applied to the analysis, and therefore, we inflated the sample size to safeguard against lost-to-follow-up

and/or crossover in the actual treatment received, which may dilute the effect size. From FASTER there were 12% crossovers and 2% losses to follow-up [8]. Most events will occur early in the follow-up period and hence a smaller fraction of events will be lost and a smaller total correction in sample size is required (5.0%). Details regarding the sample size calculation are provided in Table 1.

Table 1. Assumptions and Specifications Used to Calculate Sample Size

| Proportion with events at 90 days in placebo (aspirin) group    | 15.24%  |
|---|---------|
| Relative risk reduction (reference: placebo+aspirin group)      | 0.23    |
| Hazard Ratio  | 0.75    |
| Delay between symptom onset and enrollment                      | 12 hour |
| Loss to follow-up at 90 days (from FASTER)                      | 2%      |
| Crossovers at 90 days (from FASTER, non-event related)          | 12%     |
| Impact of crossover on events                                   | 29%     |
| Inflation factor for crossovers and losses if events at 90 days | 31%     |
| Modeled inflation factor to account for crossovers/losses       | 5.0%    |
| Power   | 0.90    |
| Total alpha (2-sided) with 2 interim analyses                   | 0.05    |

Given the uncertainty in the assumptions used to predict effect size and event rates, we have chosen a sample size to provide 90% power. With this sample, we will have 80% power to detect a relative risk reduction of 19%. Further, we will have 80% power if the placebo event rate is 23% lower than projected (see Figure 2) or early losses to follow-up are 4-times more frequent than anticipated. Power curves are shown below:

Figure 1. Minimum Detectable Relative Risk Reduction for 90% Power by Placebo Event Rate by Total Sample Size

[figure not shown]
[figure not shown]

Figure 2. Total Sample Size Needed by Placebo Event Proportion by Power

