### 5.2 Re-estimation of the Sample Size

If after 4,150 patients have been enrolled, less than 530 events have been observed, then power will be reduced. This could happen, for example, if the event rate is lower than expected in the minor stroke cohort. The power is defined by the total number of events, which depends only on the hazard ratio. For a given sample size, a decrease in event rates (overall), assuming a fixed hazard, will decrease power.

The sample size re-estimation should be based solely on the placebo event rate (not the observed difference in treatment groups). The assumed placebo rate is 15.24% with a 95% CI (13.63%, 16.85%) based on a sample of 1907 TIA patients from KPNC. At the time of the first interim analysis when approximately 1/3 of the expected number of events (177) are observed, if the one-sided upper 99% confidence limit around the observed placebo rate does not overlap with those of the assumed rate (Lower 13.63%, Upper 16.85%), then the maximum sample size will be re-estimated based on the observed placebo event rate (given a RRR of 23% as originally assumed).

Figure 2 gives the total sample size needed for a given placebo event rate at various powers. Some scenarios for stopping the trial early versus increasing the sample size are given in section 12.5 as a guide for the DSMB. The DSMB's decision to recommend an increase in the total sample size would take into account the likelihood of success of the trial using the other interim monitoring criteria (see section 12.4 for a flow chart) as well as the safety profile.

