### 12.2. Interim Efficacy Analysis

For the interim analyses of the composite event for the primary efficacy analysis, O'Brien and Fleming (1979) stopping boundaries are adopted. Assuming that the two interim analyses occur after approximately 177 (1/3 of 530 total events) and 353 (2/3) events have been observed and adjudicated, the nominal alpha levels to reject the null hypotheses for overwhelming efficacy are as follows:

POINT Trial Statistical Analysis Plan (Version 8: Sept 2017)

Table 2. Nominal Critical values and Alpha Levels for Three Interim Analysis for Overwhelming Efficacy (O'Brien-Fleming,  $\alpha$ =0.05 two-sided)

| Analysis Order | Number of Events | Nominal critical point (Z-value scale) | Alpha level |
|----------------|------------------|--|-------------|
| 1              | 177              | ±3.710                                 | 0.0002      |
| 2              | 353              | ±2.511                                 | 0.012       |
| Final          | 530              | ±1.993                                 | 0.0463      |

Depending upon the DSMB request, additional interim analyses may be conducted. The spending function approach gives flexibility in the timing and frequency of interim analyses. The most current version of the EAST® software (Cytel Corporation) is used as the interim monitoring tool.

At any interim analysis, if we cross the stopping boundary, the DSMB may recommend stopping the study for overwhelming efficacy of one treatment over the other, although the better treatment may not necessarily be clopidogrel. If and only if the stopping boundary is crossed, prior to making the final decision for recommendation to stop the study, it is expected that the DSMB would request thorough analyses of secondary outcomes and subgroup analyses to confirm the findings of the primary outcome results.

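### SAP 5.1 claims 80% power for a 19% relative risk reduction with 4,150 subjects; its own inputs give about 75%, and 80% power needs a reduction of about 20%

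*SAP*

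**What the plan says.** The design statement in SAP 5.1 is: "With a sample size of 4,150 patients, with 530 events, the study will have 90% power to detect a relative risk reduction of 23"%, with two-sided alpha 0.05. The section continues: "The sample size was estimated based on a hazard ratio (HR) of 0.75 (equivalent to RRR of 23"%), and "The total sample size for the study is 4,150 subjects (rounded up from 4,142"). Table 1 sets the placebo event proportion at 15.24% and the modelled inflation for crossovers and losses at 5.0%. The text says the size also allows for two interim efficacy looks with O'Brien-Fleming boundaries.

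After Table 1, SAP 5.1 describes how robust the design is to wrong assumptions: "With this sample, we will have 80% power to detect a relative risk reduction of 19"%. It then says that 80% power also survives a placebo rate 23% below projection, or early losses four times as frequent as expected.

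Two other places bear on the check. SAP 5.2 states: "The power is defined by the total number of events, which depends only on the hazard ratio". SAP 12.2 plans that "the two interim analyses occur after approximately 177 (1/3 of 530 total events) and 353 (2/3) events have been observed and adjudicated", and its Table 2 gives critical values of 3.710, 2.511 and 1.993.

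**The concern.** The 90% and 80% statements describe the same sample, so one constrains the other. At a fixed sample size, moving from 90% to 80% power shrinks the detectable effect by a known ratio, (1.960 + 0.842)/(1.960 + 1.282) = 0.864. Applied to 23%, this gives 19.9%, not 19%, with hardly any dependence on the event model.

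The sentence tells a reader how much protection remains if the true effect is smaller than planned. If it is wrong, the chance of missing a 19% reduction is about one in four rather than one in five.

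**Working it through.** **Inputs.** Placebo risk p0 = 0.1524, N = 4,150, 530 events, 5% inflation, two-sided alpha 0.05 and exponential survival come from SAP 5.1 and Table 1. Allocation is 1:1 (SAP 4). The final critical value of 1.993 is from SAP 12.2, Table 2; z = 1.96 is used for the version without interim looks.

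**Formulas.**
- HR = ln(1 − p0(1 − RRR)) / ln(1 − p0)
- Expected events D = N × p0 × (2 − RRR)/2, with N divided by 1.05 when the allowance is applied
- Log-rank power = Φ(|ln HR| × √(D/4) − z)

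**Step 1: reproduce the plan's own design.** RRR 23% gives HR = 0.755 and |ln HR| = 0.2811. For 90% power at z = 1.96, D = 4 × (1.960 + 1.282)² / 0.2811² = 532 events, against 530 stated. The mean event proportion is 0.1524 × 1.77/2 = 0.1349, so N = 532/0.1349 = 3,943, and × 1.05 = 4,140, against 4,142 stated. Power at RRR 23% is 89% to 91% across the variants used below.

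**Step 2: reproduce a neighbouring claim.** A placebo rate 23% lower is 0.1524 × 0.77 = 11.73%. At RRR 23% this gives 79% to 82% power, in line with the stated 80%. The claim about early losses was not tested.

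**Step 3: the 19% claim.** HR = ln(1 − 0.81 × 0.1524)/ln(1 − 0.1524) = 0.7968 and |ln HR| = 0.2271. The mean event proportion is 0.1524 × 1.81/2 = 0.1379.

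| Reading | Events | Power, z = 1.96 | Power, z = 1.993 |
|---|---|---|---|
| 4,150/1.05 subjects | 545 | 75.5% | 74.5% |
| Planned event total | 530 | 74.3% | 73.3% |
| All 4,150, no allowance | 572 | 77.5% | 76.5% |

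For the first row: 0.2271 × √(545/4) = 2.651; 2.651 − 1.993 = 0.658; Φ = 0.745. Simulating all three looks with the Table 2 boundaries gives 74.9% (545 events), 73.8% (530) and 77.0% (572). A two-proportion test gives 74.1% (4,150/1.05, z = 1.993) to 77.2% (4,150, z = 1.96).

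**Step 4: what 80% power requires.** Solving for the relative risk reduction:
- with the 5% allowance: 20.0% (z = 1.96) or 20.2% (z = 1.993);
- with 530 events: 20.2% or 20.4%;
- with all 4,150 and no allowance: 19.6% or 19.8%.

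At RRR 19%, the events needed are 4 × (z + 0.8416)²/0.2271² = 609 (z = 1.96) or 623 (z = 1.993). Dividing by 0.1379 gives 4,414 or 4,518 subjects; × 1.05 gives 4,634 or 4,744.

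**Step 5: other readings of 19%.**
- Taking it as anything up to 19.49% gives 79.7%, but only with neither allowance nor interim boundary. With both kept, power is 76.7%.
- Taking it as HR 0.81 gives 68% at 530 events.
- A one-sided 0.05 test gives 84% to 86%, but the SAP specifies two-sided.
- A 16.5% placebo proportion with no allowance gives 81.2%. However, SAP 12.1.2 gives 16.5% as the hazard rate, and −ln(1 − 0.1524) = 0.165, so it is the same assumption as the 15.24% proportion.

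**The case against.** The strongest reply is that the gap is partly one of reporting precision. If all 4,150 subjects are counted and the interim looks ignored, the reduction detectable with 80% power is 19.56%. With z = 1.993 it is 19.78%. Either would read 19% if truncated rather than rounded, and the shortfall in power on this reading is 2.5 to 3.5 points, not 5. The sentence refers to the sample, not to the sample after the allowance, so this reading is possible. But SAP 5.1 says the sample size was inflated for crossover and loss to guard against dilution of the effect. A power figure that spends that inflation as effective sample is not the power the design was built to give. With the allowance the figure is 20.0% to 20.2%, which truncation does not explain.

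The discrepancy is also smaller than the uncertainty in the inputs. SAP 5.2 gives the placebo rate a 95% confidence interval of 13.63% to 16.85%, and at about 16.1% the claim would hold with all 4,150 subjects and z = 1.96. That is true, but 16.1% is not the rate the SAP assumes.

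Finally, SAP 5.3 raises the maximum to 5,840, so the sentence now describes the original design only. This lowers its importance. It does not correct it, and it still stands in Version 8 of the SAP. The objections that remain valid are that 75% depends on applying the 5% allowance, and that no decision rests on the figure.

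**Conclusion.** The stated 80% does not follow from the SAP's inputs. With the SAP's own 5% allowance, power at a 19% relative risk reduction is about 75%; the two-sided variants run from 73.3% to 77.5%. The reduction detectable with 80% power is about 20% (19.6% to 20.4%, HR 0.791 to 0.782). This is a reconstruction. It rests on a 15.24% placebo risk, exponential survival and a two-sided 0.05 test, and it is supported by the fact that the same formulas recover the 530 events, the 4,142 subjects and the lower-placebo-rate claim.

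The consequence is minor. The 90% design power, the 530-event target, the boundaries, the conditional-power futility rule and the sample size re-estimation rule do not use the 19% figure. A 19% reduction also lies below the 23% that SAP 5.1 calls the smallest difference of clinical importance, and the result will be reported as a hazard ratio with a 95% confidence interval.

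**What to change.** Replace the sentence in SAP 5.1 with one saying that, for the 4,150-subject design, power is 80% for a relative risk reduction of about 20% (hazard ratio about 0.785) and about 75% for a reduction of 19%. State that the 5% allowance is applied, so that the basis is clear. If a matching figure is wanted for the 5,840 maximum, name the placebo rate it assumes, since neither document reports the rate observed at the first interim analysis. The cost is one sentence; the sample size, event target, boundaries and analyses are unchanged.
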